7.3 Reporting of Adverse Events and Serious Adverse Events

The Investigator is to report all AEs directly observed or spontaneously reported by subjects using concise medical terminology. Each subject will be questioned about AEs at each clinic or evaluation visit, asking, for example, “Since your last clinic visit have you had any health problems?”

The AE reporting period begins with informed consent and ends with the last scheduled study evaluation or until all drug related toxicities and ongoing SAEs have resolved, whichever is later. All AEs must be reported in the eCRF, whether or not considered related to study medication using the appropriate forms/procedure.

7.3.1 *Reporting serious adverse events*

All SAEs, events determined to be medically significant by the treating Investigator, and unknown reactions or unexpected events should be reported to the PCCTC within 24 hours of knowledge of the event using the contact information below. The initial report should include the following information at a minimum:

- protocol # and title
- subject identification number, sex, age at event
- date the event occurred
- description of the SAE
- causal relationship to the study treatment(s)

The MedWatch Form will be used for reporting each SAE and should be submitted to the PCCTC Project Coordinator with the minimum information within 24 hours. The PCCTC will facilitate all SAE report form submissions to the Sponsor-Investigator (UW PI).

Grade, relationship, action taken, concomitant medications, outcome, etc. should be reported to the PCCTC as soon as possible.

Follow-up of adverse events should continue until the event and any sequela resolve or stabilize at a level acceptable to the investigator.

SAE contact information for the PCCTC is listed below.

PCCTC:
Prostate Cancer Clinical Trials Consortium
Email: [contact]

For SAEs, the PCCTC is to be notified by the Investigator, using the designated form, **within 24 hours of the event**. The initial report is to be followed by submission of more detailed SAE information within 5 calendar days of the initial report.

The PCCTC will facilitate the notification of SAEs to Gilead Sciences, Inc. All SAEs and pregnancies should be reported to: Email: [contact]

7.3.2 *Other reporting requirements*

University of Wisconsin Carbone Cancer Center (UWCCC) site: SAEs that occur at UWCCC require reporting to the PCCTC within 24 hours, so submission to the UWCCC DSMC via an email to [contact] must be done within that same 24 hour period. The OnCore SAE Details Report must be submitted along with other report materials as applicable (UWCCC SAE Routing Form, Sponsor-Investigator Determination Form for FDA Reporting of Safety Events, FDA Medwatch Form #3500A, supporting documentation). Follow-up information for the SAE must be submitted to [contact] within 5 calendar days of the initial report.

Non-UWCCC participating sites: For SAEs occurring at non-UWCCC sites, the site will submit FDA Medwatch form 3500A and other protocol-specific SAE reporting to the PCCTC ([contact]) within 24 hours of the site being made aware of the event. The PCCTC will then forward the SAE information to the UWCCC study team ([contact]). The UWCCC study team will complete the UWCCC Sponsor-Investigator Determination Form for FDA Reporting of Safety Events.

SAE information will be entered and tracked in the UWCCC secure, password protected computer network.

Reporting to the FDA

Serious Adverse Events occurring on studies on which a UW PI is acting as sponsor-investigator must be reported to the FDA by UWCCC within the appropriate time frame. Mandatory and voluntary reporting guidelines and instructions are outlined on the FDA website: <http://www.fda.gov/Safety/MedWatch/HowToReport/default.htm>

Sponsor-Investigator Responsibilities for SAE Review

The Sponsor-Investigator (i.e., the individual who holds the IND) assumes responsibilities of the study sponsor in accordance with FDA 21 CFR 312.32. In this capacity, the Sponsor-Investigator reviews all reports of serious adverse events occurring on the study at the UWCCC and other participating sites and makes a determination of 1) **suspectedness** (i.e., whether there is a reasonable possibility that the drug caused the SAE); and 2) **unexpectedness** (the event is not listed in the Investigator's Brochure or is not listed at the specificity or severity that has been observed) in the context of this study.

Expedited Reporting

SAEs with suspected causality to study drug and deemed unexpected are reported as IND Safety Reports by the Sponsor-Investigator to FDA, all PIs participating on the study at other sites, and the external global sponsor (if applicable) within 15 calendar days. All fatal or life-threatening SAEs that are unexpected and have suspected causality to the study drug will be reported by the sponsor-investigator to FDA, all PIs participating on the study at other sites, and the external global sponsor (if applicable) within 7 calendar days.

7.4 Grading and Relatedness of Adverse Events

7.4.1 Grading of severity of an AE

The severity of each AE will be graded using the NCI CTCAE Version 4.0, which may be found at <http://ctep.cancer.gov/reporting/ctc.html>. In most cases AE terms will be listed in the CTCAE, with grading criteria specific to that term. If the AE is not specifically defined in the CTCAE, it is to be reported using the “Other, specify” term under the appropriate system organ class and graded according to the general CTCAE severity guidelines.

For each event, the highest severity grade should be reported. If a CTCAE criterion does not exist, the Investigator should use the grade or adjectives as described in **Table 8**.

Table 8. Grading of Adverse Event Severity

Grade	Adjective	Description
Grade 1	Mild	Does not interfere with subject's usual function
Grade 2	Moderate	Interferes to some extent with subject's usual function
Grade 3	Severe	Interferes significantly with subject's usual function
Grade 4	Life-Threatening	Results in a threat to life or in an incapacitating disability

A severe reaction (e.g., a severe headache) would not be classified as serious unless it met one of the criteria for SAE(s) listed above.

7.4.2 Relatedness to study drug

The investigator must attempt to determine if an AE is in some way related to the use of the study drug. This relationship should be described as follows:

Unrelated: The event has no temporal relationship to study drug administration (too early or late or study drug not taken), or there is a reasonable causal relationship between the AE and another drug, concurrent disease or circumstance.

Unlikely: The event with a temporal relationship to drug administration which makes a causal relationship improbable, and in which other drugs, chemicals or underlying disease provide plausible explanations.

Possible: The event follows a reasonable temporal sequence from administration of the study drug and the event follows a known response pattern to the study drug *BUT* the event could have been produced by an intercurrent medical condition which, based on the pathophysiology of the condition, and the pharmacology of the study drug, would be unlikely related to the use of the study drug *or* the event could be the effect of a concomitant medication.

Definite: The event follows a reasonable temporal sequence from administration of the study drug, the event follows a known response pattern to the study drug and based on the known pharmacology of the study drug, the event is clearly related to the effect of the study drug.

Reporting requirements for AEs are summarized in *Table 9*:

Table 9. Reporting Requirements for Adverse Events		
	Reporting Time	Type of Report
SERIOUS	Within 24 hours	Initial report on designated SAE form
	Within 5 calendar days of initial report	Follow-up/Final report on designated form
NON-SERIOUS	Per CRF submission procedure	Appropriate CRF pages

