Nausea	3 (3.7)	10 (3.1)	0	1 (33.3)	14 (3.3)
Vomiting	2 (2.5)	9 (2.8)	0	1 (33.3)	12 (2.9)
General disorders and administration site conditions	12 (14.8)	22 (6.7)	1 (11.1)	1 (33.3)	36 (8.6)
Fatigue	5 (6.2)	10 (3.1)	1 (11.1)	0	16 (3.8)
Pyrexia	5 (6.2)	4 (1.2)	0	0	9 (2.1)
Infections and infestations	7 (8.6)	22 (6.7)			29 (6.9)
Respiratory, thoracic and mediastinal disorders	4 (4.9)	8 (2.4)	0	0	12 (2.9)
Metabolism and nutrition disorders	2 (2.5)	8 (2.4)	0	0	10 (2.4)

Table 3: Adverse Events of \geq Grade 3 Occurring in >5% of Patients

	Any grade	\geqGrade 3	Grade 4	Grade 5
Patients, n (%)	420 (100.0)			
Patients with at least one AE	419 (99.8)	227 (54.0)	70 (16.7)	20 (4.8)
Gastrointestinal disorders	382 (91.0)	87 (20.7)	0	0
Nausea	283 (67.4)	22 (5.2)	0	0
Diarrhea	261 (62.1)	37 (8.8)	0	0

General disorders and administration. site conditions	316 (75.2)	54 (12.9)	0	5 (1.2)
Fatigue	224 (53.3)	41 (9.8)	0	0
Blood and lymphatic system disorders	277 (66.0)	109 (26.0)	49 (11.7)	0
Anemia	171 (40.7)	47 (11.2)	1 (0.2)	0
Neutropenia	171 (40.7)	75 (17.9)	43 (10.2)	0
Febrile neutropenia	25 (6.0)	18 (4.3)	5 (1.2)	0
Metabolism and nutrition disorders	266 (63.3)	76 (18.1)	8 (1.9)	0
Hypophosphatemia	51 (12.1)	22 (5.2)	1 (0.2)	0
Respiratory, thoracic and mediastinal disorders	210 (50.0)	23 (5.5)	6 (1.4)	7 (1.7)
Investigations	204 (48.6)	71 (16.9)	21 (5.0)	0
Neutrophil count decreased	77 (18.3)	41 (9.8)	13 (3.1)	0
WBC count decreased	62 (14.8)	25 (6.0)	9 (2.1)	0
Infections and infestations	179 (42.6)	38 (9.0)	3 (0.7)	2 (0.5)

Responses have been observed in subjects with triple-negative breast cancer (TNBC), small-cell lung cancer, non-small-cell lung cancer, esophageal cancer, urinary bladder, and colorectal cancer.^{37-40,49} Disease stabilization has been observed in many subjects. Since the initial results over 465 subjects (including, 32 colorectal, 147 TNBC, 60 SCLC, 46 urothelial cancer, 55 non-small cell lung cancer (NSCLC), and 52 advanced/metastatic breast cancer (Non-TNBC), have been treated with Sacituzumab Govitecan, the majority at 10mg/kg given on days 1 and 8 in a 21-day cycle.

While Sacituzumab Govitecan has not been combined with ARSIs in prior studies, fatigue is the only anticipated overlapping toxicity between these classes of agents. ARSIs have been combined with chemotherapy agents in other studies and found to be feasible.^{69,70,71}

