7. SAFETY EVALUATION

7.1 Definitions

7.1.1 *Adverse event (AE)*

All subjects must be carefully monitored for AEs, including clinical laboratory tests. AEs should be assessed in terms of their seriousness, intensity, and relationship to the study drug. For consistency, events are to be graded using the CTCAE version 4.0.

An AE is any untoward medical occurrence in a subject or clinical investigation subject administered a pharmaceutical product, and which does not necessarily have to have a causal relationship with this treatment. An AE can therefore be any unfavorable and unintended sign (including an abnormal laboratory finding, for example), symptom, or disease temporally associated with the use of a medicinal product, whether or not considered related to the medicinal product.

AEs include the following:

1. An exacerbation, or an unexpected increase in frequency or intensity of a pre-existing condition (other than condition under investigation), including intermittent or episodic conditions.
2. Significant or unexpected worsening or exacerbation of the condition/indication under investigation.
3. A suspected drug interaction.
4. An intercurrent illness.
5. Any clinical significant laboratory abnormality.

An AE does not include:

1. Anticipated day-to-day fluctuations of any pre-existing conditions, including the disease under study.
2. Signs and symptoms of the disease under study that do not represent a significant worsening or exacerbation.
3. Expected progression of the disease under investigation.

7.1.2 *Adverse drug reaction*

All noxious and unintended responses to a medicinal product related to any dose should be considered adverse drug reactions (ADRs). The phrase “responses to a medicinal product” means that a causal relationship between a medicinal product and an adverse event is at least a reasonable possibility, i.e. the relationship cannot be ruled out. Causality assessment is required for all clinical investigation cases. All cases judged by either the reporting health care professional or the sponsor as having a reasonable suspected causal relationship to the medicinal product qualify as ADRs.

7.1.3 *Unexpected adverse drug reaction*

An unexpected ADR is an AE where the nature or severity of which is not consistent with the applicable product information (e.g., Investigational Brochure, study protocol or ICF). The following documents or circumstances will be used to determine whether an AE/ADR is expected:

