7.2 Documenting Adverse Events

The investigator should elicit information regarding the occurrence of AEs through open-ended questioning of the subject, physical examination and review of laboratory results.

All AEs, whether serious or not, will be described in the source documents and the AE page of the electronic case report form (eCRF). AEs will be reported from the time of signing of informed consent, however AEs captured prior to the initial administration of Sacituzumab Govitecan will not be considered related to study drug. All new events, as well as those that worsen in intensity or frequency relative to baseline, which occur after administration of study drug through the period of protocol-specified follow-up, must be captured. AEs occurring for 30 days after the last dose of study drug must be reported. SAEs, felt by the investigator to be related to study drug, however, must be reported any time the investigator becomes aware of such an event, even if this occurrence is more than 30 days after the last dose of study drug.

Abnormal laboratory values per se need not be reported as AEs. Abnormal laboratory values that result in clinical sequelae, that require intervention, that are deemed clinically significant by the investigator or investigator's designee, that are SAEs, that result in a change in protocol treatment, or that result in study discontinuation should be reported as AEs.

Information to be reported in the description of each AE includes:

- A medical diagnosis of the event (if a medical diagnosis cannot be determined, a description of each sign or symptom characterizing the event should be recorded).
- The date of onset of the event or whether it is ongoing.

- Whether the event is serious or not.
- Action taken in response to the event.
- Action taken with study drug.
- Outcome.

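### Section 7.4.2 allows Possible or Definite only for events with a known response pattern, so a new type of toxicity cannot be rated drug-related, contrary to section 7.1.2

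*Combined protocol and SAP*

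**What the plan says.** Section 7.4.2 offers four ratings:

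- *Unrelated*: no temporal relationship or, sufficient on its own, "there is a reasonable causal relationship between the AE and another drug, concurrent disease or circumstance".
- *Unlikely*: timing that makes causation improbable, and "other drugs, chemicals or underlying disease provide plausible explanations".
- *Possible*: a reasonable sequence in time from "administration of the study drug and the event follows a known response pattern to the study drug", together with a competing explanation. That explanation is either an intercurrent condition or that "the event could be the effect of a concomitant medication".
- *Definite*: reasonable timing, and "the event follows a known response pattern to the study drug and based on the known pharmacology of the study drug" a clear relation.

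Other sections set a different standard. Section 7.1.2 treats a response as an adverse drug reaction if "a causal relationship between a medicinal product and an adverse event is at least a reasonable possibility", explained there as a relationship that cannot be excluded. Section 7.1.3 defines an unexpected reaction as one whose nature or severity does not match the product information. In section 7.3.2 the sponsor-investigator judges each SAE on reasonable possibility, and judges expectedness separately.

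Relatedness is used in four places:

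- the drug-related tables in 8.4.2, including those limited to Grade 3 and above;
- the 7.5 rule that non-serious AEs rated possibly related are followed after participation ends;
- the 7.2 rule for events more than 30 days after the last dose, where "SAEs, felt by the investigator to be related to study drug, however, must be reported any time";
- several rules in 6.4.1.

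Section 1.3 says the drug has not been given with ARSIs in earlier studies and that "fatigue is the only anticipated overlapping toxicity between these classes of agents".

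**The concern.** Whether the drug caused an event and whether the event was already known are separate questions. Sections 7.1.2, 7.1.3 and 7.3.2 keep them apart, but the investigator's scale in 7.4.2 merges them. A reaction that is unexpected in nature does not, by that fact, follow a known pattern. The protocol recognises such reactions, yet its scale leaves the site no related rating for them.

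This matters more here than for a well-characterised regimen, because most of the safety interest lies in a combination with no prior data. If sites follow the definitions literally, new toxicities are left out of the drug-related tables. Their non-serious cases also lose the follow-up that 7.5 attaches to a possibly related rating.

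**Working it through.** The point concerns definitions, and the plan has no figure to reproduce. The check describes an event by three features and applies each 7.4.2 definition in turn:

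- T: reasonable timing after dosing;
- K: known response pattern to the study drug;
- A: a reasonable alternative cause (another drug, a disease or a circumstance).

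| Event | T | K | A | Ratings whose definition is met |
|---|---|---|---|---|
| New toxicity, no other cause | yes | no | no | none |
| New toxicity, another reasonable cause | yes | no | yes | Unrelated (or Unlikely, if the timing makes causation improbable) |
| Known toxicity, no other cause | yes | yes | no | Definite, if clearly related |
| Known toxicity, another possible cause | yes | yes | yes | Possible; arguably also Unrelated |
| No reasonable timing | no | any | any | Unrelated, or Unlikely where A also holds |

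**Row 1.** Unrelated fails because timing is reasonable and there is no other cause. Unlikely fails because causation is not improbable and no other explanation exists. Possible and Definite both fail on K. Possible fails a second time because it also requires a competing explanation. The scale is therefore not exhaustive.

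**Row 2.** K again bars Possible and Definite. The other-cause part of Unrelated is joined to the timing part by *or*, so it is met alone. By contrast, 7.1.2 calls the same event an adverse drug reaction whenever drug causation is a reasonable possibility, whether or not another cause exists.

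**Row 4.** Unrelated asserts that a reasonable causal relationship with another drug exists. Possible says a concomitant medication could be the cause. Section 6.5 lists the continued ARSI under concomitant therapy. For fatigue in a man on both drugs, two careful investigators could choose differently.

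**Comparison of standards.** Section 7.1.2 and the suspectedness test in 7.3.2 both ask for a reasonable possibility, and neither mentions a known pattern. Only 7.4.2 adds that condition, so 7.4.2 is the section out of line.

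**The case against.** Much of the safety system does not depend on this rating, and these counterpoints stand:

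- Section 7.3.1 sends SAEs, medically significant events, and reactions that are unknown or unexpected to the PCCTC within 24 hours, whatever their rating. Section 7.3.2 gives SAEs their own reasonable-possibility review, which drives IND safety reports.
- All AEs are recorded (7.3). Section 8.4.2 also tabulates all AEs and all Grade 3 or higher AEs, and stratifies safety by whether the ARSI was continued. Those tables need no attribution.
- Section 7.2 names no 7.4.2 category for late SAEs. For men still in follow-up, 5.7 collects deaths and hospitalizations in any case. The dependence on the rating is confined to men who came off for progression, whose follow-up closes after the AE check at least 30 days after the last dose (Appendix B, note 7).
- In 6.4.1, some rules apply regardless of relationship to the drug or state no relatedness condition. The Table 7 note leaves unrelated events to the investigator's discretion.

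Three stronger readings are tempting, and the documents do not support them:

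- *No ARSI interaction could be rated related.* An interaction that only worsens a known toxicity still follows a known pattern and can be rated Possible. The bar applies to new patterns.
- *Unrelated and Possible plainly contradict each other for shared toxicities.* One asserts another cause and the other leaves it open, so Possible is the more natural reading for fatigue of uncertain origin. This is an ambiguity.
- *The fatigue rates in Table 3, multiplied by 55, give the number of men misrated.* Those rates are all-causality and pooled over doses, and the 55 include men on monotherapy who started before amendment 5. The product would count fatigue, not misratings.

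None of the safeguards changes the rating of a new non-serious event, the drug-related tables, or follow-up under 7.5.

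**Conclusion.** The point holds as a contradiction between a stated rule and the protocol's own definition of a drug reaction. One type of well-timed event has no rating at all. A second, with a reasonable alternative cause, can only be rated Unrelated or Unlikely, even where drug causation is a reasonable possibility.

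The consequence is incomplete attribution. Safety events are not lost from the database, and expedited reporting is not blocked. The places affected are the drug-related tables, post-study follow-up of non-serious AEs, late SAE reports for men out of follow-up, and those rules in 6.4.1 that turn on relatedness. No number of affected events can be given, because the documents do not say how often new toxicities occur.

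Two assumptions underlie this. Investigators apply 7.4.2 as written. And Possible and Definite are the ratings that count as drug-related, since 8.4.2 does not say which do. The change should be made, but the trial's validity does not depend on it.

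**What to change.** Reword 7.4.2 to match 7.1.2:

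1. Define Possible as a reasonable temporal sequence plus a reasonable possibility that the study drug caused the event. Deleting the known-pattern condition alone is not enough: Possible would still require a competing explanation, and the event in row 1 would still have no rating.
2. Leave expectedness to 7.1.3.
3. Limit the other-cause part of Unrelated to events where a contribution of the study drug can be ruled out. This also settles the boundary for toxicities shared with the ARSI.

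Under this wording, the events in rows 1 and 2 can be rated Possible whenever drug causation is a reasonable possibility. A separate eCRF item for relatedness to the ARSI would help describe the combination but is optional.

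The cost is protocol wording and site retraining. Somewhat more events will count as drug-related. Because some rules in 6.4.1 refer to relatedness, they must be checked for consistency with the new wording. No change to those rules is proposed here.

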7.4.3 Recording information on AEs

All AEs, whether observed by the Investigator, elicited from, or volunteered by the subject, will be recorded including: duration, severity, relationship to the study medication, treatment, action taken with respect to the study medication and outcome. When possible, all events should be reported in diagnostic terms or the most acceptable medical terms in order to interpret safety information accurately.

The investigator must review all laboratory test data and record any AEs. The same format will be used as for other AEs, regardless whether related to study therapy or not, including event severity grading, attribution, and resolution. A summary listing of all AEs occurring during the past year on this study will be provided in progress reports reported to regulatory authorities.

